106 **IX. Demographic/Patient Specific Data Collected**

107 Age, sex, ASA score, height, weight, body mass index, and comorbidities will be collected.

108 **X. Primary Outcome Measure**

109 - Functional component of the 2012 version KSS at time of consenting and at 3 weeks and 6
 110 weeks following surgery

111 **XI. Secondary Outcome Measures**

112 - A timed up and go (TUG) test before surgery at time of consenting and at 3 weeks and 6
 113 weeks following surgery. The TUG test consists of measuring the time it takes for an
 114 individual to rise from a seated position in a chair, walk to a mark 3 meters away, turn
 115 around, come back, and sit in the same chair from which they started. Patients will be asked
 116 to perform the test twice at each of the aforementioned encounters. The use of any assistive
 117 devices such as cane or a walker) will also be noted.

118 - Occurrence of any of the Knee Society's Standardized List of Complications³¹ (Table 1)

119 **XII. Patients and Protocols**

120 Patients will be enrolled from the clinics of [name] and [name] [name], two
 121 fellowship-trained orthopedic surgeons in the division of Adult Reconstruction at Midwest
 122 Orthopedics at Rush University Medical Center. Study staff will screen the clinic schedule of
 123 each surgeon and will discuss the purposes of the investigation at the time of their visit. If the
 124 patient is willing to participate in the investigation, verbal and written consent will be obtained
 125 by the study staff. At the time of consenting, patients will also be asked to perform a TUG test
 126 and will be asked to complete the questions that comprise the functional component of the KSS
 127 score.

128 This study will be tripled-blinded, thus, the patients, clinicians, and research staff
 129 involved will be unaware of patient allocation during this study. Each patient will receive a study
 130 ID, and a computer randomization system will be used to randomize a list of numerical IDs to
 131 either the treatment or control arm. Study IDs will then be written on medication envelopes, and
 132 a member of the clinical team, who is not involved in this study, will then place either the
 133 treatment drug (Vitamin D) or placebo (empty, opaque gelatin capsule) into the envelopes based
 134 on the ID assignment. Only this clinical team member who is not involved in the study will

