 135 possess the list matching the study ID to the study group assignment, ensuring that the study
 136 remains triple-blinded and that study coordinators are unaware of a patient's assignment when he
 137 or she picks up the study medication.

138 Patients randomized to the experimental arm of the study will receive 50,000IU of
 139 vitamin D₃ before surgery and asked to take the medication orally before surgery. Vitamin D₃
 140 was selected over vitamin D₂ as the former is less expensive and is more effective at raising
 141 serum 25-OH vitamin D levels than the latter.³² The regimen of 50,000IU given once was
 142 selected as this regimen has been previously used without side effects in previous studies and
 143 has been shown to be as effective as other regimens that utilize more frequent dosing with
 144 smaller doses.^{29, 30, 33} Patients randomized to the control arm will receive placebo tablets of
 145 empty, opaque gelatin capsules and advised to consume their medication similar to the
 146 treatment arm. Both groups of patients will receive their medications from the pharmacy at
 147 Rush Medical Center, which will be responsible for providing patients with the appropriate
 148

151 regimen. All patients will receive the same postoperative multimodal analgesic regimen that is
152 normally administered to patients undergoing THA and TKA at Rush University Medical Center.
153

154 In accordance with current standard post-operative care, patients will be asked to follow-
155 up with their surgeon in clinic at 3 weeks and 6 weeks following surgery. At these post-operative
156 visits, patients will be asked to repeat the TUG test and the 19 questions of the functional
157 component of the KSS score.

158 **XIII. Sample Size**

159 Utilizing data from previous studies, an *a priori* power analysis revealed that 45 patients
160 in each cohort are required to detect a minimally clinically important difference (MCID) of 6
161 points in the functional component of the updated, 2012 KSS version with an assumed standard
162 deviation of 10 points. A difference of 6 points was set as the MCID as that is the value found in
163 a previous study evaluating the previous version of the KSS using patient satisfaction and
164 Oxford Knee Scores as anchors.³⁴ To the best of our knowledge, there are no studies that have
165 quantified the MCID for the 2012 KSS yet. Assuming a 10% drop out rate, we will require 50

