166 patients per group for a total of 100 patients overall.

167 **XIV. Treatment and Control Groups**

168 *Numbers reflect an assumed 10% drop out rate

169 Intervention Group: n=50

170 Control Group: n=50

171 **XV. Risks/Benefits**

172 The major risk of patients enrolled in this study stem from potential side effects of
173 hypercalcemia secondary to hypervitaminosis D. Symptoms that have been reported are
174 nausea, dehydration, constipation, polyuria, polydipsia, anorexia, vomiting and muscle
175 weakness. However, documented cases of hypercalcemia due to hypervitaminosis D all involved
176 intake of greater than 40,000IU per day for an extended period of time, and supplementation is
177 widely regarded to be safe in doses under 10,000IU per day for less than 12 weeks^{35, 36}—amounts
178 that are significantly below our proposed dosage. In addition, Binkley et al reported no adverse
179 effects or episodes of toxicity in patients who were supplemented our proposed dosage of
180 50,000IU monthly for one year.³³

181 A risk inherent to every study is the potential for breach of confidentiality and/or
182 privacy. Below is a description of the precautions for maintaining confidentiality.

183 Due to a lack of studies, the benefits of vitamin D supplementation in patients undergoing
184 orthopedic procedures remains unknown. The only study to supplement patients of
185 all vitamin D levels found no differences in functional scores post-operatively among those who
186 did and did not receive supplementation. Based on the many studies demonstrating the negative
187 association between vitamin D deficiency on post-operative outcomes and the benefits of
188 supplementation in patients with knee osteoarthritis, we speculate that supplementation will
189 vitamin D will improve both in patients undergoing total knee arthroplasty with minimal risk of
190 adverse effects.

191 **XVI. Procedures for Maintaining Confidentiality**

192 A breach of confidentiality and/or privacy is a risk of this study. To prevent this, all
193 collected data will be stored electronically in password-protected files to protect patient identity
194 and information. All information will be collected and reviewed by the research team only. Data
195 will be maintained on a password-protected computer that will be accessible only to the study
196 team. No patient identifiers will be maintained in the database.

202
203
204
205
206
207

XVII. Budget

Item	Cost

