Vitamin D (50,000IU tablet for 50 patients)	\$17.40
Placebo of Empty, Opaque Gelatin tablets (50 patients)	\$5.69
Total* * All values were provided by the pharmacy at Rush University Medical Center	\$23.09

208
209
210
211
212

213
214**XVIII. Tables and Figures****Table 1 . Knee Society Complication List**

Complication/Adverse Event	Definition
1. Bleeding	Postoperative bleeding requiring surgical treatment
2. Wound complication	Failure of wound healing requiring reoperation or a change in TKA protocol
3. Thromboembolic disease	Symptomatic thromboembolic event requiring more intensive, nonprophylactic anticoagulant or antithrombotic treatment during the first 3 months after index TKA
4. Neural deficit	Postoperative neural deficit (sensory or motor) related to the index TKA
5. Vascular injury	Intraoperative vascular injury requiring surgical repair, bypass grafting, or stenting (compartment syndrome or amputation should be reported)
6. Medial collateral ligament injury	Intraoperative or early postoperative medial collateral ligament injury requiring repair, reconstruction, a change in prosthetic constraint, revision surgery, or TKA protocol
7. Instability	Symptomatic instability reported by the patient and confirmed by laxity on physical examination as defined by The Knee Society Knee Score
8. Misalignment	Symptomatic malalignment reported by the patient and confirmed radiographically with angular deformity in the coronal plane [10° from the mechanical axis]
9. Stiffness	Limited ROM as reported by the patient and demonstrated in a physical examination with extension limited to 15° short of full extension or flexion $< 90^\circ$ (not applicable if preoperative arc of motion $< 75^\circ$)
10. Deep periprosthetic joint infection	A deep periprosthetic joint infection can be diagnosed when there is a sinus tract communicating with the prosthesis; or a pathogen is isolated by culture from at least two separate tissue or fluid samples obtained from the affected prosthetic joint; or 4 of the following 6 criteria exist: elevated ESR and serum CRP concentration; elevated synovial WBC count; elevated synovial PMN; presence of purulence in the affected joint; isolation of a microorganism in one culture of periprosthetic tissue or fluid; or >5 neutrophils/high-power field in 5 high-power fields observed from histologic analysis of periprosthetic tissue at 9400 magnification

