11. Periprosthetic fracture	Periprosthetic fracture of the distal femur, proximal tibia, or patella (operative or nonoperative treatment should be recorded).
12. Extensor Mechanism Disruption	Disruption of the extensor mechanism (surgical repair and/or extensor lag should be recorded)
13. Patellofemoral dislocation	Dislocation of the patella from the femoral trochlea (direction of instability should be recorded)
14. Tibiofemoral dislocation	Dislocation of the tibiofemoral joint (direction of instability should be recorded)
15. Bearing surface wear	Wear of the bearing surface symptomatic or requiring reoperation
16. Osteolysis	Expansile lytic lesion adjacent to one of the implants 1 cm in any one dimension or increasing in size on serial radiographs/CT scans

17. Implant loosening	Implant loosening confirmed intraoperatively or identified radiographically as a change in implant position or a progressive, radiolucent line at the bone-cement or bone-implant interface
18. Implant fracture or tibial insert dislocation	Implant fracture or dissociation of the tibial insert from the tibial implant
19. Reoperation	Return to the operating room related to the index TKA (reasons for reoperation should be recorded)
20. Revision	Revision of one or more of the TKA implants (femur, tibia, tibial insert, patella)
21. Readmission	Admission to the hospital for any reason during the first 90 days after TKA (reasons for admission and relation to index TKA should be recorded)
22. Death	Death occurring for any reason during the first 90 days after TKA (cause of death and relation to index TKA should be recorded)

215

216

217

218 **XIX. References**

219 1. Wacker M, Holick M. Vitamin D—effects on skeletal and extraskeletal health and the need for
220 supplementation. *Nutrients*. 2013;5(1):111-48.

221 2. Morrison RJM, Bunn D, Gray WK, Baker PN, White C, Rangan A, et al. VASO (Vitamin D and
222 Arthroplasty Surgery Outcomes) study - supplementation of vitamin D deficiency to improve outcomes
223 after total hip or knee replacement: study protocol for a randomised controlled feasibility trial. *Trials*.
224 2017 Nov 2;18(1):514. Epub 2017/11/04.

225 3. Piuazzi NS, George J, Khlopas A, Klika AK, Mont MA, Muschler GF, et al. High prevalence and
226 seasonal variation of hypovitaminosis D in patients scheduled for lower extremity total joint arthroplasty.
227 *Ann Transl Med*. 2018 Aug;6(16):321. Epub 2018/10/27.

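### Three Table 1 complications are defined to 90 days or 3 months, but no patient contact or record review is described after the 6-week visit

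*Combined protocol and SAP*

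**What the plan says.** Section XI lists as a secondary outcome the "Occurrence of any of the Knee Society's Standardized List of Complications" and refers to Table 1 in Section XVIII. Unlike the Knee Society Score (KSS) function component and the timed up and go (TUG) test, this outcome is given no assessment time and no method of collection.

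Three Table 1 definitions contain a fixed window:

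- Item 3, thromboembolic disease: a symptomatic event needing more intensive "anticoagulant or antithrombotic treatment during the first 3 months after index TKA".
- Item 21, readmission: "Admission to the hospital for any reason during the first 90 days after TKA".
- Item 22, death: "Death occurring for any reason during the first 90 days after TKA".

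Section XII gives the follow-up. After surgery, patients are asked to follow "up with their surgeon in clinic at 3 weeks and 6 weeks following surgery". The tasks named for those visits are the TUG test and the 19 KSS function questions; complications are not mentioned. No later contact appears anywhere. Chart abstraction is mentioned only in Section VIII, for laboratory values used in the exclusion criteria.

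**The concern.** An outcome defined to day 90 needs a source of information that reaches day 90. The described follow-up stops at about day 42. A patient admitted to another hospital on day 60, or treated there for a clot, meets the trial's own definition, yet nothing in the plan would bring the event to the study's attention.

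What is at stake is how the complication results can be read. These three items are among the most serious in the table, and the protocol describes no other collection of adverse events. If few or no events are recorded and the table is reported under the printed definitions, readers will take the counts as 90-day counts although the data behind them may end near week 6.

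**Working it through.** The plan gives no figure for the share of each window that is covered, so there is none to reproduce. Its one computed figure, 45 per group raised to 50 for 10% dropout (45 / 0.90 = 50), concerns the KSS and does not enter here.

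**Inputs**

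- Window for items 21 and 22: 90 days (Table 1).
- Window for item 3: 3 months (Table 1), taken as 91 days.
- Last planned contact: 6 weeks (Section XII), nominally 6 × 7 = 42 days.
- Visit tolerance: not stated. Days 35 to 49 are assumed, that is, one week either side.

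**Formula:** share without planned contact = (window − day of last visit) / window.

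| Day of last visit | 90-day window | 3-month window (91 days) |
|---|---|---|
| 35 | 55/90 = 61.1% | 56/91 = 61.5% |
| 42 (nominal) | 48/90 = 53.3% | 49/91 = 53.8% |
| 45 | 45/90 = 50.0% | 46/91 = 50.5% |
| 49 | 41/90 = 45.6% | 42/91 = 46.2% |

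Taking 3 months as 92 days changes the nominal figure to 50/92 = 54.3%. The gap is more than half the window at the nominal visit day and falls to half of the 90 days if the visit slips to day 45. It stays large throughout the range.

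**From days to events.** This step cannot be made from the document, which gives neither an event rate nor the timing of events. Purely as an illustration, suppose that 2 to 10 of the 100 patients have such an event and that 30% to 53% of events fall after day 42 (early-weighted risk up to constant risk). The number exposed to being missed is then 2 × 0.30 = 0.6 up to 10 × 0.53 = 5.3. That spread reflects the assumptions and is not an estimate for this trial.

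**Other sources.** Three possible routes to late events were looked for. A later visit or call: none is described. Chart review for complications: none is described. Complication questions at the 3- and 6-week visits: none are listed, so even the first 42 days have no stated method of collection.

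**The case against.** The strongest reply is that the plan is silent rather than contradictory. The complications outcome has no stated end date, and nothing says that capture stops at week 6. The windows sit inside definitions adopted from a published list and say which events count; they do not promise follow-up. Hospital records could reveal later events. All of that stands. A reader might infer that the schedule contradicts the definitions, or that late events would be entered as event-free. The document supports only that they could be missed, because no route to them is described. Unplanned use of the local chart would also not reliably capture admissions or deaths elsewhere, and item 21 counts admission for any reason.

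A reader might also infer from Section XVI ("team. No patient identifiers will be maintained in the database") that later look-up is impossible. That does not follow. Keeping identifiers out of the database does not rule out a separate link, and repeated measures under one study ID need one in practice.

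Nor is there support for reading this as a biased comparison between arms. The schedule is the same for both and the trial is blinded, so the expected effect is an under-count in each arm. Finally, the plan makes no explicit claim of 90-day safety, and its hypothesis is confined to 3 and 6 weeks. The risk arises only when counts are reported under the printed definitions.

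**Conclusion.** The point holds as a gap in ascertainment for part of a secondary outcome. With the last visit at day 42, about 53% of the 90-day window and 54% of the 3-month window have no planned contact or described data source; for the 90-day items the range is 46% to 61% for a visit at day 49 to day 35. Late readmissions, deaths and thromboembolic events could go unrecorded in both arms, and the resulting counts would not support the definitions under which they are reported.

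The percentages rest on the printed windows, the nominal visit day and the assumed one-week tolerance. They measure time without planned contact, not the share of events lost. The primary outcome and the sample size are untouched. The gap should be closed before complication results are reported, but it does not threaten the trial's main comparison.

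**What to change.** Choose one of two routes and write it into Sections XI and XII.

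1. **Extend ascertainment.** Add one telephone call at day 90 with a chart check, made by existing study staff who remain blinded, done identically in both arms and limited to items 3, 21 and 22. For item 3, make the contact late enough to cover the full 3 months. State that the link between study ID and patient is stored apart from the database until this is complete. Cost: about 100 short calls and chart checks (50 + 50 patients), no extra clinic visit, and final data later by about 48 / 7 ≈ 7 weeks.

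2. **Shorten the window.** Restate the three items as events up to the 6-week visit, add questions about them to the 3- and 6-week visits, and report them as 6-week rather than 90-day counts. Cost: wording and a few questions at visits already planned.

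Under either route, one sentence should say how and until when the rest of the complication list is collected, since the current visit description does not cover it.
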